10.6 Multiple Comparisons

Does not apply.

11. STATISTICAL EVALUATION

11.1 Subject Disposition

Subjects who enroll (ITT population), who apply any study medication, who complete the study and who withdraw from the study (together with the reasons for withdrawal) will be summarized by counts and percentages. Subjects for whom drug was permanently withdrawn or interrupted due to AE, PGA score or other reasons will also be summarized by counts and percentages, over the entire study and by visit.

Counts will be presented overall and by DB treatment group. Listings by subject will document enrollment and disposition.

The number of days in the study, defined as date of study completion / discontinuation (or date of last visit if the study completion/discontinuation date is missing) minus date of Visit 1 plus 1, will be summarized using descriptive statistics overall and by DB treatment group. A figure with Kaplan-Meier curves will also be generated to illustrate this information.

11.2 Protocol Deviation

Protocol deviations will be listed by subject. Protocol deviation categories will be summarized overall and by DB treatment group.

11.3 Demographic and Baseline Characteristics

Demographics and baseline characteristics will be summarized overall and by DB treatment group over the ITT population. The following demographic (as collected in pivotal studies) and baseline variables will be included:

- Age (years)
- Gender
- Race
- Ethnicity
- Weight (kg)
- Height (cm)
- BMI (kg/m²)
- Baseline PGA – current study and pivotal study
- Baseline PASI score – current study and pivotal study
- Baseline %BSA Affected – current study and pivotal study

11.4 Study Medication Exposure and Compliance

Subjects will be characterized by a series of treatment episodes as defined in Section 11.7. These treatment episode definitions are based on attainment of specified PGA values.

The following exposure and compliance parameters will be summarized descriptively over the overall span of treatment episodes, overall and by DB treatment group:

- Total expected number of days exposed, calculated as the sum of number of days over all treatment episodes.
- Total number of doses administered within treatment episodes, calculated from the subject dose diary and summed over all treatment episodes. If a subject does not return diary or returns the diary with missing dosing record, the number of doses taken during that period is assumed to be 0.
- Grams (g) of study drug administered within treatment episodes, total will be summed over all treatment episodes. Drug administered is calculated as the summation of the difference between dispensed weight and returned weight for all returned tubes. Unreturned tubes will be assumed unused and will be included as 0 gram in amount drug used calculation. Average grams of study drug administered per expected day exposed and per doses administered will be calculated as the total grams / total number of days exposure (or total number of doses administered). Subjects with more than 1-day exposure but had no diaries returned will not have average grams per doses administered reported.
- Percent compliance will be calculated as the total number of doses administered within treatment episodes over the total expected number of days exposed.
- Subject compliance, defined as $\geq 80\%$ compliance over the entire duration of study. If the percentage of study medication compliance is unknown, the subject is assumed to be non-compliant with study medication.

In addition, the following exposure parameters will be summarized descriptively for the entire study (regardless of PGA status) overall and by DB treatment group:

- Total number of doses administered, calculated from the subject dose diary and in-clinic dosing. If a subject does not return diary or returns the diary with missing dosing record, the number of doses taken during that period is assumed to be 0.
- Grams (g) of study drug administered. Drug administered is calculated as the summation of the difference between dispensed weight and returned weight for all returned tubes. Unreturned tubes will be assumed unused and will be included as 0 gram in amount drug used calculation. Average grams of study drug administered per doses administered will

be calculated as the total grams / total number of doses administered. Subjects that had no diaries returned will not have average grams per doses administered reported.

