4.6.1. Reasons for Withdrawal from Study

Study drug will be discontinued for any of the following reasons:

- Subject has an AE that is considered to be related to study drug or procedures AND is severe enough to warrant treatment discontinuation, as determined by the Investigator (Section 8.1)
- Subject requires concurrent prohibited concomitant medication during the study. If, in the opinion of the Investigator and the study Medical Monitor, such medication will not interfere with the conduct or interpretation of the study or compromise the safety of the subject, then the subject may continue to receive study drug. If the subject is discontinued from study drug, they may remain in the study for safety assessments as needed, at the discretion of the Investigator and Medical Monitor.
- Pregnancy
- Any Grade 3 or 4 AE considered causally related to study drug (Section 8.2.2)

Study drug may be discontinued for any of the following reasons:

- Subject noncompliance
- Investigator noncompliance
- Discontinuation of the study at the request of the Sponsor, regulatory agency, or an Institutional Review Board (IRB)/Independent Ethics Committee (IEC)

If a subject meets a withdrawal criterion during treatment, an Early Termination Visit will be required (Section 7.7).

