8.1.3. Adverse Events of Special Interest

In prior clinical studies, the following AEs have been identified as AEs of particular clinical importance and will be reported as AESIs in this study; in each case, study drug may be discontinued, and study drug may be restarted when event resolves:

- Contact dermatitis: the study site should collect location, duration, size, associated symptoms (itching, burning, pain), severity (mild, moderate, severe), and photograph the affected site (if possible). If the subject contacts the study site to report significant skin irritation at or near the site of study drug application between study visits, the subject should be brought for an unscheduled visit, if possible.
- Folliculitis: the study site should collect the location, duration, size, associated symptoms (itching, burning, pain), severity (mild, moderate, severe), indicate whether pustular, and photograph the affected site (if possible)
- Headache: the study site should collect duration, severity (mild, moderate, severe), onset, and location

Additional AESIs may be identified by the Drug Safety Physician and if applicable by the Clinical Study Team Physician during the evaluation of safety data for the Clinical Study Report. For each AESI, a narrative may be written and included in the Clinical Study Report.

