11.7 Efficacy Endpoints

Efficacy endpoints are as follows:

For subjects entering the study with a PGA score of clear (0):

- Proportion of subjects who experience PGA ≥ 2 at least 1 time during the study.
- Proportion of subjects who never experience PGA ≥ 2 throughout the study.
- Time to first worsening (PGA ≥ 2), defined as days from date of Visit 1 date to the date of first occurrence of PGA ≥ 2 . Subjects who never experience PGA ≥ 2 throughout the study will be censored at the date of their last PGA assessment.

For subjects entering the study with a PGA score ≥ 1 :

- Proportions of subjects who achieve PGA = 0 at least 1 time during the study

• [REDACTED]

• [REDACTED]

[REDACTED]

For subjects entering the study with a PGA score ≥ 2 :

- Proportions of subjects who achieved PGA = 0 or 1 at least 1 time during the study.
- Proportions of subjects who never achieve PGA = 0 or 1 throughout the study.

The following endpoints will be summarized over subjects in ITT population:

- Duration (days) of treatment episodes, defined as time (days) from the date of each PGA ≥ 2 (or PGA ≥ 1 for the first episode) to 1 day before each subsequent treatment success (PGA = 0). The date of the last PGA assessment will be used as the end date for episodes ongoing at the end of the study.

- [REDACTED]
- [REDACTED] \geq [REDACTED]
- [REDACTED]
- [REDACTED]
- [REDACTED]
- [REDACTED] change and percent change from baseline in %BSA affected by visit (OC and LOCF).
- [REDACTED] change and percent change from baseline in PASI score by visit (OC and LOCF)
- [REDACTED] \geq [REDACTED]
- [REDACTED] \geq [REDACTED]
- [REDACTED] \geq [REDACTED]

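### SAP 11.4 keeps days off drug for an adverse event in expected exposure, which understates percent compliance and grams per expected day for the affected subjects

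*SAP*

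**What the plan says.** SAP 11.4 sets the expected exposure time as "Total expected number of days exposed, calculated as the sum of number of days over all treatment episodes". It says of the episodes: "These treatment episode definitions are based on attainment of specified PGA values". SAP 11.7 opens an episode at a PGA of 2 or more (1 or more for the first episode) and closes it the day before PGA 0. If PGA 0 is not reached, "The date of the last PGA assessment will be used as the end date for episodes ongoing at the end of the study". Neither section mentions dosing status.

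The same sum of days is then used three times in SAP 11.4. "Percent compliance will be calculated as the total number of doses administered within treatment episodes over the total expected number of days exposed". A subject is compliant at 80% or more over the whole study. Average grams are also given per expected day.

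The protocol allows drug to be stopped inside an episode. Section 4.6.2 permits interruption for skin irritation during an active course. Section 8.1.3 says that for contact dermatitis, folliculitis and headache "study drug may be discontinued, and study drug may be restarted when event resolves". SAP 11.1 counts subjects for whom "drug was permanently withdrawn or interrupted due to AE, PGA score or other reasons", but SAP 11.4 makes no use of that information.

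**The concern.** A day on which the subject was told not to apply the cream is not a day on which a dose was expected. Under SAP 11.4 it is counted as one if it falls inside a PGA-defined episode, and it then looks the same as a missed dose.

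The SAP treats two permitted kinds of stop differently. Days off drug after PGA 0 lie outside any episode and are not expected days. Days off drug for an adverse event are equally permitted but remain expected. SAP 11.1 names both reasons side by side.

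The effect is not spread evenly. It falls on subjects with local reactions or other adverse events, in a study whose first objective is safety and tolerability. In the compliance table, part of what is a tolerability effect will read as poor adherence.

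**Working it through.** The plan states no figure to reproduce, so the check applies the SAP 11.4 formula directly.

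**Inputs from the documents**
- Expected days E: total days over all PGA-defined episodes (SAP 11.4, 11.7).
- Cut-off: 80% over the whole study (SAP 11.4).
- Longest treatment: 40 weeks × 7 = 280 days (Protocol synopsis).
- Visits about every 28 days (Protocol 5.1.5.2), so E = 28, 56, 84 and so on are natural values.

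**Assumptions (not in the documents)**
- g: days off drug on instruction within episodes, varied from 7 to 84.
- a: adherence on days when dosing was allowed, 100% or 90%.

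**Formulas**
- SAP percent compliance = a(E − g)/E.
- With off-drug days deducted = a(E − g)/(E − g) = a.
- With m missed doses on allowed days, doses = E − g − m. The subject fails 80% when (E − g − m)/E < 0.80, that is, when g + m > 0.20E.
- Grams per expected day is multiplied by (E − g)/E, so it falls by g/E.
- Expected days exceed the days on which dosing was allowed by E/(E − g) − 1.

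**Results under the SAP formula**

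| E | g | a = 100% | a = 90% | Excess of expected over allowed days |
|---|---|---|---|---|
| 28 | 7 | 75.0% | 67.5% | 33.3% |
| 56 | 7 | 87.5% | 78.8% | 14.3% |
| 56 | 14 | 75.0% | 67.5% | 33.3% |
| 84 | 14 | 83.3% | 75.0% | 20.0% |
| 112 | 28 | 75.0% | 67.5% | 33.3% |
| 280 | 28 | 90.0% | 81.0% | 11.1% |
| 280 | 56 | 80.0% | 72.0% | 25.0% |
| 280 | 84 | 70.0% | 63.0% | 42.9% |

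For example, (56 − 14)/56 = 42/56 = 75%, and grams per expected day is 14/56 = 25% lower than grams per allowed day. By contrast, (280 − 56)/280 = 224/280 = 80%, which meets the cut-off. With the deduction, every row gives 100% or 90% and every subject is compliant.

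The longest stop that leaves a fully adherent subject compliant is 5 days for E = 28, 11 for 56, 16 for 84, 22 for 112, 33 for 168 and 56 for 280. E is the whole-study total. A 56-day row therefore describes a subject with 56 expected days in all, not one 56-day episode among several.

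**After permanent discontinuation.** Protocol 4.6.1 requires an Early Termination visit when a withdrawal criterion is met during treatment, and Protocol 7.7 includes a PGA at that visit. If it is the last PGA, SAP 11.7 ends the open episode there, and the overcount is the gap from last dose to that visit. The gap is longer if a later PGA is recorded.

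**The case against.** The strongest reply has four parts.

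First, a reader might infer that anyone who obeyed an instruction to stop is recorded as exposed and non-compliant. The documents do not support that. The 80% rule is applied to the whole study, and short stops in long treatment stay compliant. Doses and total grams come from diaries, in-clinic dosing and tube weights, so they do not treat an off-drug day as dosed. The affected day count is labelled as expected. This stands, and the point is limited accordingly.

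Second, a reader might cite Protocol 4.6.1, "If the subject is discontinued from study drug, they may remain in the study for safety assessments as needed", as showing long off-drug follow-up after an adverse event. That sentence belongs to the item on prohibited concomitant medication, not to the adverse-event items. It does not carry that argument. Temporary interruption is the firmer ground.

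Third, interruptions for adverse events are not hidden. SAP 11.1 tabulates them over the study and by visit. SAP 11.11.1 lists the action taken with drug and summarises actions taken for each adverse event of special interest. This also stands. But those outputs do not correct the compliance figure or say how much of a shortfall comes from ordered stops.

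Fourth, doses over all episode days is a legitimate relative-exposure measure, in keeping with other cautious rules in SAP 11.4 such as counting an unreturned diary as zero doses. That is fair as a reason to keep the measure. It is not a reason to let it stand alone as subject compliance.

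**Conclusion.** The point holds in a limited form. As written, SAP 11.4 understates percent compliance and grams per expected day for subjects whose drug was interrupted for an adverse event. It also does so, normally for a short tail only, after permanent discontinuation. The understatement of both measures is the fraction g/E. A change of class needs ordered off-drug days plus missed doses above 20% of whole-study expected days.

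How many subjects this affects cannot be said, because the documents give neither the frequency nor the length of interruptions; the figures above are illustrations. Parts of SAP 11.7 are redacted, but the treatment-episode definition is legible.

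The severity is minor. All analyses use the ITT set, there is no statistical testing, and compliance is neither a listed endpoint nor a subgroup factor. A reader might also infer that the ICH E1 exposure counts in SAP section 9 are inflated. The SAP does not say that those counts use expected days, so that does not follow.

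**What to change.** In SAP 11.4, do one of the following:

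- subtract from expected days the documented days of adverse-event interruption, and the days after permanent drug discontinuation, that fall inside an episode; or
- keep the present measure and report percent compliance, the 80% class and grams per expected day both with and without that deduction.

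The second option is preferable, since it keeps the relative-exposure measure and shows adherence beside it. Doses in the numerator should be counted over the same days as the denominator. In either case, add a row for days lost to adverse-event interruption, overall and by double-blind treatment group. No clinical rule changes.

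The cost is SAP wording and some extra derivation. The deduction depends on interruption start and stop dates. Protocol 4.6.2 has a safety interruption documented in the eCRF, and SAP 11.11.1 lists action taken with drug, but neither states that both dates are captured. This should be confirmed before the rule is written. If the dates are not captured, the SAP should say how diary and action-taken records are combined. The diary alone is not enough, because SAP 11.4 sets missing dosing records to zero doses whatever the reason.

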- On study visit days, study drug should be applied in the clinic under the supervision of site personnel and after safety assessments have been completed

NOTE: The time of the dose and assessments on study visit days will depend on the time of the study visit (either morning or afternoon visit). Therefore, the timing of the study visit may differ from the subject's chosen dosing time (morning or evening); if

this occurs, it should not be recorded as a protocol deviation and the subject should resume their chosen dosing time following any such study visit. The intention is to allow flexibility to accommodate subjects' schedules.

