5.4. Compliance with Study Drug Administration

At baseline, study staff will provide the subject with detailed instructions concerning protocol requirements and use of study drug in this extension study. Additionally, subjects will be asked to complete a daily diary with the time of each application of study drug. At each postbaseline study visit, study staff will review use of study drug, as applicable, with the subject.

When subjects are dosed at the site, they will apply the study drug under supervision of the study staff. The date and time of each dose administered in the clinic will be recorded in the source documents. The study drug and study subject identification will be confirmed at the time of dosing by a member of the study site staff.

At the time of dispensing study drug to each subject, site personnel will weigh the tubes to be dispensed and will record the weight of all tubes dispensed at each visit in the drug accountability logs. Subjects will be instructed to bring all used and unused tubes with them to each study visit. Site personnel will weigh the returned tubes (used and unused) and record the weight in the drug accountability logs. If a tube has been lost, discarded, or forgotten by the subject, the site personnel will make a notation of this on the drug accountability logs. The site personnel will remind the subject to keep all tubes of study drug dispensed and to bring all used and unused tubes to each study visit. These data will be used to estimate subject compliance with use of study drug. Tubes of study medication dispensed at the most recent prior visit, which remain unopened (the foil cap on the tube remains fully intact/undisturbed) may be redispensed to study subjects at the current visit. Unopened tubes may only be dispensed one time. Opened, partially used tubes, or tubes with foil overlay removed are not to be redispensed to study subjects. If there is any question as to redispensation, sites should issue new tubes of study medication to the subject(s).

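### SAP 11.4 takes the compliance numerator from the diary alone, so supervised clinic doses missing from a returned diary are scored as missed

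*SAP*

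**What the plan says.** SAP 11.4 counts doses twice, from different sources. The within-episode count is "Total number of doses administered within treatment episodes, calculated from the subject dose diary and summed over all treatment episodes". The whole-study count is "Total number of doses administered, calculated from the subject dose diary and in-clinic dosing".

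The first count feeds compliance: "Percent compliance will be calculated as the total number of doses administered within treatment episodes over the total expected number of days exposed". It is also the divisor for within-episode grams per dose. The compliance denominator is "Total expected number of days exposed, calculated as the sum of number of days over all treatment episodes", and nothing removes visit days from it. Under SAP 11.7 an episode starts on the date of a qualifying PGA, which is a visit date, and runs "to 1 day before each subsequent treatment success (PGA = 0". The starting visit and all intermediate visits are therefore inside the episode, and the success visit is outside it. For episodes still open, "The date of the last PGA assessment will be used as the end date for episodes ongoing at the end of the study".

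On where visit-day doses are given and recorded, Protocol 5.1.5.3 says "On study visit days, study drug should be applied in the clinic under the supervision of site personnel", and Protocol 5.4 says "The date and time of each dose administered in the clinic will be recorded in the source documents". Protocol 5.4 also asks subjects to log the time of every application in the diary, without saying whether clinic applications are included.

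**The concern.** The numerator and the denominator may not cover the same days. Each visit day on treatment adds one expected day. The dose given that day enters the numerator only if it also appears in a diary that comes back. The doses at risk of being dropped are those that site staff watched and documented. Naming in-clinic dosing separately in the whole-study count suggests that the SAP authors did not expect the diary to hold all of them.

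At stake are the percent-compliance summary, the flag for at least 80% compliance, and the within-episode grams per dose. All three describe exposure in a study whose sample size rests on an exposure guideline.

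**Working it through.** The documents give no compliance result to reproduce; 80% is a rule. The check is direct arithmetic.

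**Inputs**
- Visits every 4 weeks (Protocol 3.1), so one clinic dose per 28 days on drug, ignoring the ±3-day window and unscheduled visits.
- Over 280 treated days: 10 clinic doses, at Day 1 and the nine visits from Week 4 to Week 36 (Schedule of Assessments).
- Cut-off: at least 80% (SAP 11.4).

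**Formulas.** For one episode of *k* complete cycles, with *x* doses taken including all *k* clinic doses:
- true adherence = *x* / 28*k*
- reported compliance with clinic doses absent from the diary = (*x* − *k*) / *D*, where *D* is the number of episode days
- *D* = 28*k* if days are counted inclusively, or 28*k* − 1 if they are a plain date difference.

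**1. Full adherence (*x* = 28*k*)**

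| Reading | 1 cycle | 10 cycles |
|---|---|---|
| Clinic doses not in diary, inclusive days | 27/28 = 96.4% | 270/280 = 96.4% |
| Clinic doses not in diary, date difference | 27/27 = 100% | 270/279 = 96.8% |
| Clinic doses in a returned diary, inclusive days | 28/28 = 100% | 280/280 = 100% |

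A shorter episode loses more on the first reading. A 14-day episode started at an unscheduled visit gives 13/14 = 92.9%.

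**2. The 80% flag (clinic doses not in diary, inclusive days)**
- 280 days: (*x* − 10)/280 ≥ 0.80 requires *x* ≥ 234. Subjects who took 224 to 233 doses (224/280 = 80.0% to 233/280 = 83.2%) meet the cut-off in truth but are flagged non-compliant.
- 28 days: (*x* − 1)/28 ≥ 0.80 requires *x* − 1 ≥ 22.4, so *x* ≥ 24. The smallest *x* that truly meets 80% is 23 (23/28 = 82.1%). Only that count changes class, because it is reported as 22/28 = 78.6%.

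**3. An unreturned diary.** The SAP sets doses to 0 for the period. Take four cycles at full adherence with one diary missing, and assume each diary period contains one clinic dose.
- Clinic doses in the diary: (112 − 28)/112 = 75.0%. Restoring the lost clinic dose gives 85/112 = 75.9%.
- Clinic doses not in the diary: (112 − 27 − 4)/112 = 72.3%. Restoring all four clinic doses also gives 75.9%.

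A documented dose is therefore lost on either reading of the diary. Most of the fall below 100% comes from the 27 home doses set to zero.

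**4. Within-episode grams per dose.** If the supervised dose comes from the weighed tubes and is not in the diary, its weight is counted but the dose is not: 28/27 = 1.037, or +3.7%.

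**5. With clinic doses added once each.** Inclusive days give 28*k*/28*k* = 100% for every *k*. A plain date difference gives 28/27 = 103.7% for one cycle and 280/279 = 100.4% for ten. The day count has to be fixed together with the dose count.

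**The case against.** A reader might infer that a fully adherent subject can never reach 100%, and that some subjects are certainly misclassified. The documents do not support that. It requires clinic doses to be absent from the diary, yet Protocol 5.4 asks for every application, and recording a dose in source documents does not exclude a diary entry. It also requires inclusive day counting. SAP 11.1 writes the plus 1 out for days in the study, but SAP 11.7 does not for episodes, and with a plain date difference a one-cycle episode reads 27/27.

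A reader might also infer that the two dose definitions contradict each other, or that the whole-study total counts up to 10 clinic doses twice. Both need the two sources to be simply summed. The SAP names them as sources and does not say that they are added. If the diary were complete, a diary count and a combined count with each dose taken once would agree.

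It is fair to add that the effect is small, that its direction understates adherence in line with the SAP's other cautious rules, and that nothing downstream uses the flag. Only an ITT set is defined (Protocol 10.3, SAP 7) and there is no statistical testing (SAP 10.1).

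These points limit the finding but do not remove it. The SAP does not say what the diary contains and has no rule for a clinic dose that the diary lacks. Where a diary is not returned, the clinic dose is dropped whatever the diary practice was.

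**Conclusion.** The point holds in a limited form. The compliance numerator names one source, the whole-study count names two, and the denominator includes days dosed in the clinic. Any clinic dose not in a returned diary is scored as missed.

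The shortfall is 3.6 percentage points for complete 28-day cycles, assuming clinic doses are absent from the diary and days are inclusive. On those assumptions the 80% flag is wrong only in a narrow band: 80.0% to 83.2% over 280 days, and the single count 23/28 in one cycle. If the diary holds every clinic dose and is returned, there is no bias. The documents give no adherence distribution, so the number of subjects affected cannot be estimated. The 3.7% for grams per dose also assumes that the supervised dose comes from the weighed tubes.

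Efficacy and safety results do not change. Two other rules can distort the same measure more. One is the zero-dose rule for missing diaries. The other is the end date of open episodes: if the last PGA is at the Week 44 follow-up (Day 309), full adherence reads 270/309 = 87.4% from the diary alone, and 280/309 = 90.6% even with clinic doses included.

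**What to change.** In both lists of SAP 11.4, define doses administered as the number of distinct calendar days with a dose in the diary or in the in-clinic dosing record. Count each day once, and still count clinic doses when a diary is missing. For the within-episode figures, count only days inside episodes. Define episode days as end date minus start date plus 1, so that the ratio cannot exceed 100%. Apply these definitions to percent compliance, the 80% flag and both grams-per-dose figures. State in the SAP whether clinic doses were entered in the diary.

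The cost is a wording change and a merge of dosing records that the SAP already uses for the whole-study total; no new data are needed. The change does not restore home doses from unreturned diaries and does not settle the end date of episodes open at Week 40. Those need their own decisions.

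### SAP 11.4: grams per dose is biased for subjects who return only some of their diaries or tubes, because the two zero rules act independently

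*SAP*

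**What the plan says.** SAP 11.4 defines one set of exposure measures within PGA-defined treatment episodes and a second set for the entire study regardless of PGA status.

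- **Doses.** These come from the diary. If a diary is not returned, or comes back with records missing, "the number of doses taken during that period is assumed to be 0". Both sets carry this rule.
- **Grams.** "Drug administered is calculated as the summation of the difference between dispensed weight and returned weight for all returned tubes". For the other tubes, "Unreturned tubes will be assumed unused and will be included as 0 gram in amount drug used calculation". Both sets carry this rule too.
- **Ratios.** Grams per dose is total grams over total doses. The within-episode set also gives grams per expected day of exposure, where expected days are the summed lengths of the treatment episodes.
- **Exclusions.** Within episodes: "Subjects with more than 1-day exposure but had no diaries returned will not have average grams per doses administered reported". For the entire study: "Subjects that had no diaries returned will not have average grams per doses administered reported".
- **Compliance.** "Percent compliance will be calculated as the total number of doses administered within treatment episodes over the total expected number of days exposed". A subject is compliant at 80% or more, and unknown compliance is classed as non-compliant.
- **Dose source.** The entire-study count is "calculated from the subject dose diary and in-clinic dosing". The within-episode count names only the diary.

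Protocol 5.4 has subjects bring back every tube and has sites weigh them and note any that are missing. It does not say that a missing tube is an unused one. It also lets tubes still unopened be handed out again at the next visit.

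**The concern.** The numerator and denominator of grams per dose are each filled in with zeros by their own rule, and nothing requires them to describe the same dispensing intervals. If the tubes come back without the diary, the cream counts but the applications do not, and the ratio is too high. If the diary comes back without the tubes, the ratio is too low. The exclusion deals with the case where every diary is missing and leaves all partial cases in the average.

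The figure describes how much cream an application takes, in a study whose first objective is safety and tolerability. Partial returns are foreseeable. Protocol 10.2 expects about 300 of some 850 subjects to complete, and SAP 11.12 plans to summarize virtual, telephone and missed visits due to COVID-19, whereas tubes and diaries are collected at study visits.

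**Working it through.** The plan states no grams-per-dose value, missing-diary rate or unreturned-tube rate, so there is no figure of its own to reproduce. The check applies the Section 11.4 formulas directly.

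**Inputs from the documents**
- Up to 40 weeks of treatment with visits every 4 weeks (SAP 3): 280 days, ten intervals of 28 days.
- The zero rules, exclusions and 80% cut-off (SAP 11.4).

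**Assumptions**
- The subject is on drug for all 280 days and uses the same amount in every interval. This is needed only to turn one interval of ten into a share of 0.1.
- Returned diaries and weights are accurate.

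**Formulas.** Let G be true grams, N true doses, m the share of N in missing-diary periods, u the share of G in unreturned tubes, and a true adherence.
- Grams per dose, reported/true = [G(1 - u) / N(1 - m)] / (G/N) = (1 - u)/(1 - m).
- Total grams and grams per expected day, reported/true = 1 - u.
- Reported compliance = a(1 - m). Tube weights do not enter.

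**Grams per dose, one subject**

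| Diaries missing (of 10) | Tube intervals unreturned (of 10) | Reported/true |
|---|---|---|
| 1 | 0 | 1/0.9 = 1.11 |
| 3 | 0 | 1/0.7 = 1.43 |
| 5 | 0 | 1/0.5 = 2.00 |
| 9 | 0 | 1/0.1 = 10 |
| 0 | 1 | 0.90 |
| 0 | 3 | 0.70 |
| 3 | 1 | 0.9/0.7 = 1.29 |
| 1 | 3 | 0.7/0.9 = 0.78 |
| 2 | 2 | 0.8/0.8 = 1.00 |

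The nine-diary case is still reported, because one diary came back. The factor of 10 applies to the diary-only count. If the entire-study count keeps one supervised dose in each of the nine missing periods, doses are 28 + 9 = 37 and the factor is 280/37 = 7.6.

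**Effect on a mean, for assumed shares of subjects affected.** If 10%, 20% or 30% of subjects miss three of ten diaries and the rest are complete, the mean of individual reported/true ratios is 1 + q(1/0.7 - 1): 4.3%, 8.6% or 12.9% too high. If the same shares leave three of ten tube intervals unreturned, it is 1 - 0.3q: 3%, 6% or 9% too low.

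**Grams per expected day.** The factor runs from 0.90 to 0.50 with one to five tube intervals unreturned, and is never above 1.

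**Compliance.** A fully adherent subject with three of ten diaries missing scores 196/280 = 70%; with two missing, 224/280 = 80%, which still passes. At a = 0.90, two missing give 0.90 x 0.80 = 72%. The cut-off is missed once m exceeds 1 - 0.8/a: 20% (56 days) at a = 1.00, 15.8% (44 days) at 0.95, 11.1% (31 days) at 0.90.

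**In-clinic doses.** If the diary omits one supervised dose per 28 days, within-episode compliance is at most 27/28 = 96.4%, a loss of up to 1/28 = 3.6 points.

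**The case against.** Four arguments against the point have weight.

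1. **The damage is limited.** A reader might infer that the exposure figures as a whole are wrong. The documents do not support that. Expected days use neither rule. Subjects with complete returns are correct, and equal missing shares cancel in grams per dose. As far as these two rules go, total doses and total grams are lower bounds, resting on assumptions that the SAP states openly. This stands.

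2. **Zero for a missing diary is a recognised cautious convention for compliance.** It matches the SAP's treatment of unknown compliance as non-compliant, and it cannot flatter adherence. This stands as a reason to keep the figure. It does not justify the same zero as a divisor, where it inflates grams per dose.

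3. **No safety result depends on these figures.** A reader might infer that assuming unreturned tubes unused biases the safety findings in the drug's favour. SAP 11.11.1 counts subjects with events, with no rate per gram or per dose. The ICH E1 targets in SAP 9 count subjects by treatment duration. Protocol 6.5 plans no pharmacokinetics, so grams applied are not a measure of systemic exposure. Undercounting grams could even raise apparent risk per unit of cream. This stands.

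4. **The diary may already hold the in-clinic doses.** Protocol 5.4 asks for a diary time for every application. Simply adding clinic doses could count them twice. This stands, so the in-clinic point is a request for one defined source.

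Sites log missing tubes, diaries are reviewed at visits, and derived values are listed by subject. These steps help to spot odd values but do not change how the averages are computed.

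**Conclusion.** The point holds for grams per dose in subjects with partly returned diaries or tubes. The bias is (1 - u)/(1 - m) and runs in either direction. For a single subject with ten equal intervals, it ranges from -10% for one unreturned tube interval and +11% for one missing diary to a tenfold overstatement in the extreme case that the exclusion still lets through. Total grams and grams per expected day are understated by the share u.

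Compliance is a separate and narrower matter. It might look as though both zero rules distort it, but only the diary rule does. The consequence is that an adherent subject with enough missing diaries is classed as non-compliant.

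The single-subject sizes assume constant use over 280 days on drug. The group means also rest on assumed shares of affected subjects. Without missing rates, the size in the reported tables cannot be stated. These are descriptive summaries, and no hypothesis test or planned adverse-event incidence depends on them. The point is worth correcting because the stated rule gives a biased number and the data for a better one are already collected.

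**What to change.** Amend SAP 11.4 as follows.

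1. **Grams per dose.** Use only dispensing intervals with a returned diary and all tubes returned. Link an unopened tube that is dispensed again to the interval in which it was used. Report the number and share of intervals excluded. In the illustration with three diaries missing and tubes missing for one other interval, six matched intervals remain and the ratio is 0.6/0.6 = 1.00.
2. **Total grams and grams per expected day.** Report both under the current 0 g rule and with each unreturned tube counted as fully used (labelled content 30 g, Protocol 5.1.1). The two results form a range for the unreturned tubes.
3. **Compliance.** Keep the figure with missing counted as zero, and show compliance over diary-covered days beside it. The fully adherent subject above would then show 70% and 196/196 = 100%.
4. **Dose source.** Use one definition for the within-episode and entire-study counts, with each in-clinic dose counted once.

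The cost is SAP wording and programming, with no new data. The downside is that the per-dose average rests on fewer intervals, drawn from subjects who return materials more completely, and assumes similar use in the excluded intervals. The diary-covered compliance figure makes the same kind of assumption, which is why it should accompany the current one and not replace it.
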